#### **4.7. Overnight Closed-Loop study in Children and Adolescents with Type 1 Diabetes in Home Setting**

Following successful demonstration of safety and efficacy of closed-loop insulin delivery in the research facility, overnight closed-loop studies under free living conditions were commenced in July 2012. The first study compared the efficacy and

safety of closed-loop with sensor augmented pump therapy in 16 adolescents (37). Closed-loop was activated over at least 4 hours on 269 nights (80%); sensor data were collected over at least 4 hours on 282 control nights (84%). Closed-loop increased the time when glucose was in target range by a median 15% (interquartile range -9 to +43),  $P<0.001$ . Mean overnight glucose was reduced by a mean  $0.8\pm3.2\text{mmol/l}$ ,  $P<0.001$ . Time when glucose was below 3.9mmol/l was low in both groups but nights with glucose below 3.5mmol/l for at least 20min were less frequent during closed-loop (10% vs. 17%,  $P=0.01$ ). Despite lower total daily insulin doses by a median 2.3 (interquartile range -4.7 to +9.3) units,  $P=0.009$ , overall 24h glucose was reduced by a mean 0.5 (standard deviation 2.3)mmol/l ( $P=0.006$ ) during closed-loop.

## **4.8. Overnight Closed-Loop Study in Adults with Type 1 Diabetes in Home Setting**

We completed a four week overnight closed-loop study under free living conditions in 24 adults with type 1 diabetes on insulin pump therapy in a multicentre crossover study design (38). Closed-loop was utilised over median 8.3 (interquartile range 6.0, 9.6) hours on 555 nights (86%). The proportion of time when overnight glucose was in target range between 3.9 and 8.0mmol/l from midnight to 07:00 was significantly higher during closed-loop compared to sensor augmented pump therapy ( $52.6\%\pm10.6$  vs.  $39.1\%\pm12.8$ , mean $\pm$ SD;  $p<0.001$ ). Mean overnight glucose ( $8.2\pm0.9$  vs.  $9.0\pm1.3\text{mmol/l}$ ,  $p=0.005$ ) and time spent above target ( $44.3\%\pm11.9$  vs.  $57.1\%\pm15.6$ ,  $p=0.001$ ) were significantly lower during closed-loop. Time spent below target was low and comparable between interventions [ $1.8\%(0.6, 3.6)$  vs.  $2.1\%(0.7, 3.9)$ ,  $p=0.28$ ].

A multicentre crossover RCT comparing 12 week overnight closed-loop with 12 week sensor augmented pump therapy in 24 children and adolescents aged 6 to 18 years has been completed recently; data analysis is underway.

## **4.9. Day and Night Closed-Loop Studies in Adults with Type 1 Diabetes in Home Setting**

We completed a seven day, day and night home study in 17 suboptimally controlled ( $\text{HbA1c}>7.5\%$ ) adults with type 1 diabetes in a multicentre, multi-national crossover study design (39). During the home phase, the percentage time when glucose was in target range was significantly higher during closed-loop compared to sensor augmented pump therapy ( $75 [61, 79]$  vs.  $62 [53, 70]\%$ , median [IQR],  $p=0.005$ ). Mean glucose (8.1 vs. 8.8 mmol/l,  $p=0.027$ ) and time spent above target ( $p=0.013$ ) were lower during closed-loop while time spent below target was comparable ( $p=0.339$ ).

Increased time in target was observed during both day-time ( $p=0.017$ ) and night-time ( $p=0.013$ ). A two centre multinational crossover study comparing day and night closed-loop with usual pump therapy during free-living settings was completed in 29 adults with well-controlled ( $\text{HbA1c}<7.5\%$ ) type 1 diabetes (40). The proportion of time when sensor glucose concentration was in target range was significantly increased during closed-loop delivery compared with usual pump therapy ( $65.6\pm8.1$  vs  $76.2\pm6.4\%$ ,  $p<0.0001$ ). Compared with usual pump therapy, closed-loop delivery also reduced the proportion of time spent in hypoglycaemia: the proportion of time with glucose concentration below 3.5 mmol/L was reduced by 65% (53 to 74,  $p<0.0001$ ) and below 2.8 mmol/L by 76% (59 to 86,  $p<0.0001$ ). No episodes of serious hypoglycaemia or other serious adverse events occurred.

We completed a 12-week day and night multicentre, multi-national crossover design home study in 33 adults with T1D (18 male, age  $40.0\pm9.4$  years, duration of diabetes  $20.9\pm9.3$  years) (41). The proportion of time when sensor glucose was in target range between 3.9 and 10.0 mmol/l was significantly increased during closed-loop compared to sensor augmented pump therapy ( $67.7\pm10.6$  vs.  $56.8\pm14.2\%$ ,  $p<0.001$ ). Mean glucose (8.7 vs. 9.3 mmol/l,  $p<0.001$ ) and time spent above ( $p<0.001$ ) and below target range ( $p=0.02$ ) were significantly reduced during closed-loop. Hypoglycaemia exposure measured by AUC <3.5 mmol/l was reduced during closed-loop ( $p<0.001$ ). Reduction in mean glucose and time spent above target range during closed-loop was brought about without changing the total daily insulin delivery ( $p=0.57$ ).

#### **4.10. Automated Closed-Loop System (CamAPS FX) to be used in the Present Study**

The automated closed-loop system (CamAPS FX) will consist of:

- Dexcom G6 (Dexcom, San Diego, CA, USA) or similar Continuous Glucose Monitoring (CGM) System
- Dana R Diabecare (Sooil Corp. Seoul, South Korea) or similar subcutaneous insulin infusion pump
- An Android smartphone hosting CamAPS FX Application with the Cambridge model predictive control algorithm and communicating wirelessly with the insulin pump

An overview of this proposed automated closed-loop system is given in Figure 1.

Figure 1. CamAPS FX comprises Samsung Galaxy phone (or similar) running Cambridge control algorithm, Dana insulin pump (Sooil), G6 real-time CGM sensor (Dexcom).

#### 4.11. Rationale for the Current Study

No study thus far has specifically evaluated use of closed-loop insulin delivery in older adults with type 1 diabetes. The current study will provide further evidence on the effect of consecutive closed-loop day and nights over 4 months in a group of older subjects with type 1 diabetes in a multicentre and multi-national setting to demonstrate the generalisability of results.

### 5. Objectives

#### 5.1. Efficacy

To assess efficacy of day and night automated closed-loop glucose control in maintaining glucose levels within the target range from 3.9 to 10.0 mmol/l based on subcutaneous continuous glucose monitoring (CGM) as compared to sensor augmented insulin pump therapy alone.

## **5.2. Safety**

To evaluate the safety of automated closed-loop glucose control in terms of episodes and severity of hypoglycaemia and nature and severity of other adverse events.

## **5.3. Utility**

To determine the percentage of time when closed-loop was operational.

## **5.4. Human Factors**

To evaluate the expectations, attitudes and behaviours that influence the uptake and response to using a closed-loop system, and sleep quality.

## **5.5. Cardiac Rhythm**

To evaluate cardiac arrhythmic events with concordant CGM sensor glucose values during closed-loop system use and sensor-augmented pump therapy.

## 6. Study Design

An open-label, multi-centre randomised, two-period crossover study comparing day and night automated closed-loop glucose control with sensor-augmented pump therapy.

It is expected that up to 42 older subjects with type 1 diabetes with T1D will be recruited, aiming for 36 randomised subjects. Subjects who drop out within the first six weeks of the intervention may be replaced. The study flow chart is outlined in Figure 2.

## 7. Study Subjects

### 7.1. Study population

[figure not shown]
This is a multicentre and multinational study and recruitment will take place at the following centres:

1. Addenbrooke's Hospital, Cambridge, UK
2. Manchester Royal Infirmary, Manchester, UK
3. Queen Elizabeth Hospital, Birmingham, UK
4. Medical University of Graz, Graz, Austria

Adults aged 60 years or over with type 1 diabetes on insulin pump therapy will be recruited. The study will aim for 36 completed subjects. Recruitment will target up to 42 subjects (8 - 20 subjects per centre) to allow for drop-outs. Methods of patient recruitment will follow well established practice at each centre.

Potential participants will be identified by their treating clinicians and invited to contact the research team. They will be sent the study information leaflets and an invitation to join the study by the research team at least one day before the recruitment visit.

Figure 2. Study flow chart.

### **7.1.1. Inclusion criteria**

1. Age 60 years and above
2. Type 1 diabetes as defined by WHO for at least 1 year or is confirmed C-peptide negative
3. On insulin pump for at least 3 months with good knowledge of insulin self-adjustment
4. Treated with one of the U-100 rapid acting insulin analogues only (insulin Aspart, Lispro, Faster insulin Aspart but not Glulisine)
5. Willing to perform regular capillary blood glucose monitoring
6. HbA1c ≤ 10% (86 mmol/mmol) based on analysis from central laboratory or equivalent
7. Literate in English
8. Having a care partner who is aware of the subject's location and is trained to administer intramuscular glucagon and able to seek emergency assistance
9. Willing to wear closed-loop system at home and at work place
10. Willing to follow study specific instructions
11. Willing to upload pump and CGM data at regular intervals
12. Has access to WiFi

### **7.1.2. Exclusion criteria for all countries**

1. Non-type 1 diabetes mellitus
2. Use of a closed-loop system within the last 30 days
3. Any other physical or psychological disease or condition likely to interfere with the normal conduct of the study and interpretation of the study results
4. Commencement of any glucose-lowering agent (such as Pramlintide, Metformin, GLP-1 analogs) in the 3 months prior to enrolment or any use of SGLT2 inhibitors
5. Untreated coeliac disease, adrenal insufficiency or hypothyroidism
6. Known or suspected allergy against insulin
7. More than one episodes of severe hypoglycaemia as defined by American Diabetes Association (42) in preceding 6 months
8. Random C-peptide > 200pmol/l with concomitant plasma glucose >4 mmol/l (72 mg/dl)
9. Lack of reliable telephone facility for contact
10. Total daily insulin dose ≥ 2 IU/kg/day

11. Total daily insulin dose < 15 IU/day
12. Severe visual impairment
13. Severe hearing impairment
14. Medically documented allergy towards the adhesive (glue) of plasters or unable to tolerate tape adhesive in the area of sensor placement
15. Serious skin diseases (e.g. psoriasis vulgaris, bacterial skin diseases) located at places of the body, which could potentially be used for localisation of the glucose sensor)
16. Subject is currently abusing illicit drugs
17. Subject is currently abusing prescription drugs
18. Subject is currently abusing alcohol
19. Subject has elective surgery planned that requires general anaesthesia during the course of the study
20. Subject is a shift worker with working hours between 10pm and 8am
21. Subject has a sickle cell disease, haemoglobinopathy; or has received red blood cell transfusion or erythropoietin within 3 months prior to time of screening
22. Subject plans to receive red blood cell transfusion or erythropoietin over the course of study participation
23. Subject diagnosed with current eating disorder such as anorexia or bulimia
24. Subject plans to use significant quantity of herbal preparations (use of over the counter herbal preparation for 30 consecutive days or longer period during the study) or significant quantity of vitamin supplements (four times the recommended daily allowance used for 30 consecutive days or longer period during the study) known to affect glucose metabolism and/or blood glucose levels during the course of their participation in the study
25. Subject not proficient in English (UK), or German (Austria)

### **7.1.3. Additional exclusion criteria specific for Austria**

1. Positive results on urine drug screen (amphetamines/metamphetamines, barbiturates, benzodiazepines, cannabinoids, cocaine, opiates).
2. Positive alcohol breath test.
3. Positive reaction to any of the following tests: hepatitis B surface (HBs) antigen, anti-hepatitis C virus (anti-HCV) antibodies, anti-human immunodeficiency virus (HIV) 1 antibodies, anti-HIV2 antibodies.

## **7.2. Randomisation**

The order of closed-loop or sensor-augmented pump therapy will be randomly allocated using block randomisation within a centrally administered randomisation programme. Randomisation will take place within 1 week before the start of first home study phase.

# **8. Methods under Investigation**

## **8.1. Name and description of the method of investigation**

The investigational treatment is the CamAPS FX, see section 4.10, or follow up prototypes of the automated day and night closed-loop system manufactured by the Cambridge University Hospitals NHS Foundation Trust. Component versions will be identified during regulatory submission to the MHRA and relevant authority in Austria.

## **8.2. Intended purpose**

The intended purpose of the investigational treatment is automated day and night closed-loop insulin delivery.

## **8.3. Method of administration**

The closed-loop system consists of components directly attached to the patient, which are the CGM transmitter and the insulin pump. The component not directly attached to the patient is the handheld smartphone containing closed-loop algorithm and communicating wirelessly with the insulin pump.

## **8.4. Required training**

Prior to commencement of the study, the research team nurses/clinicians at each of the investigation centres will be trained to use the closed-loop system and its components. Prior to the use of study devices, participants will be trained to use the study CGM device, the study pump and where appropriate the closed-loop system. This can be done face to face or remotely as required. Competency assessments of the participants' capability to use study devices and the closed-loop system will be made.

## **8.5. Precautions**

During treatment with insulin there is a risk of hypoglycaemia and hyperglycaemia. In-hospital testing and Hazard Analysis both documented reduced risk of hypoglycaemia

and hyperglycaemia during day and night closed-loop compared to sensor-augmented pump treatment.

## **8.6. Accountability of the method under investigation**

The local Investigator will provide training for the study participants and will make every effort, through regular contact, to ascertain that the closed-loop system is used for the study purposes only. Devices will be identified using batch/lot/serial numbers and the location of investigational devices and their dates of use by subjects will be documented throughout the study.

# **9. Study Schedule**

## **9.1. Overview**

The study will be coordinated from the Institute of Metabolic Science, University of Cambridge, and performed at the following sites

1. Addenbrooke's Hospital, Cambridge, UK
2. Manchester Royal Infirmary, Manchester, UK
3. Queen Elizabeth Hospital, Birmingham, UK
4. Medical University of Graz, Graz, Austria

The study will consist of up to 19 visits or pre-planned telephone/email contacts including two study periods (closed-loop vs. sensor-augmented pump therapy). The study periods will last 4 months each. The order of the two interventions will be in random order.

The visit to set up automated closed-loop for the first time may take place in the study or clinical facility or can be done remotely. All other visits can take place at the hospital clinic, home or other suitable meeting place or remotely, according to participants' convenience. Two 16-week study periods will be performed within four weeks of each other. Maximum time in study is 12 months.

Table 1 outlines study activities when CL intervention precedes sensor-augmented pump therapy.

Table 2 outlines study activities when sensor-augmented pump therapy precedes CL intervention.

*Table 1. Schedule of study visits when closed-loop intervention precedes sensor-augmented pump therapy.*

	Visit/ contact	Description	Start relative to previous / next Visit / Activity	Duration
	*Visit 1	Recruitment visit: Consent HbA1c, baseline bloods, 12-lead ECG, human factor assessment	-	1-3 hours
Study Pump & CGM Training /Run-In	*Visit 2	Insulin pump training and initiation of study pump Competency assessment	Can be combined with Visit 1, or within 1 to 3 weeks of Visit 1	3-4 hours
	*Visit 3	CGM training Initiation of CGM Competency assessment	Within 7 days of Visit 2. Can coincide with Visit 2	1 hour
	*Visit 4	Review pump and CGM data & compliance assessment & Randomisation	After 3 - 4 weeks of Visit 3	1-2 hours
CL Intervention (4 months)	*Visit 5	CL initiation at CRC or remotely - CL training & competency assessment - HbA1c	Can be combined with Visit 4, or within 2 week of Visit 4	Up to 6 hours
	* Visit 6	Review use of study devices	After 24-48 hours of Visit 5	<1 hour
	*Visit 7	Review use of study devices	After 1 week of Visit 5	<1 hour
	*Visit 8	Review pump and CGM data	After 1 week of Visit 7	<1 hour
	*Visit 9	End of first month; Review pump and CGM data.	After 4 weeks of Visit 5	<1 hour
	*Visit 10	End of second month; Review pump and CGM data. Actiwatch sleep monitor	After 4 weeks of Visit 9	<1 hour
	*Visit 11	End of third month; Review pump and CGM data.	After 4 weeks of Visit 10	<1 hour
	*Visit 12	12-lead Holter monitor applied for 5-7 days.	Within 14 days after Visit 11.	<1 hour

			Can coincide with Visit 11	
	*Visit 13	End of closed-loop treatment period (4 months). HbA1c. Collect algorithm device. Revert back to usual diabetes therapy. Human factor assessment.	After 4 weeks of Visit 11	1-2 hours
	-	Washout period	Immediately after Visit 13	4 weeks
Control Intervention (4 months)	*Visit 14	Control therapy initiation at CRC or remotely - Sensor-augmented pump refresher training & competency assessment - HbA1c	After 4 weeks of end of Visit 13	Up to 6 hours
	*Visit 15	End of first month. Review of home data.	After 4 weeks of Visit 14	<1 hour
	*Visit 16	End of second month. Review of home data. Actiwatch sleep monitor	After 4 weeks of Visit 15	<1 hour
	*Visit 17	End of third month. Review of home data.	After 4 weeks of Visit 16	<1 hour
	*Visit 18	12-lead Holter monitor applied for 5-7 days.	Within 14 days after Visit 17. Can coincide with Visit 17	<1 hour
	*Visit 19	End of open-loop treatment period (4 months) HbA1c. Human factor assessment	After 4 weeks of Visit 17	1-2 hours

\*Could be done via phone / e-mail in UK.

*Table 2. Schedule of study visits when sensor-augmented pump therapy precedes closed-loop intervention.*

	Visit/ contact	Description	Start relative to previous / next Visit / Activity	Duration
	*Visit 1	Recruitment visit: Consent HbA1c, baseline bloods, 12-lead ECG, human factor assessment	-	1-3 hours
Study Pump & CGM Training /Run-In	*Visit 2	Insulin pump training and initiation of study pump Competency assessment	Can be combined with Visit 1, or within 1 to 3 weeks of Visit 1	3-4 hours
	*Visit 3	CGM training Initiation of CGM Competency assessment	Within 7 days of Visit 2. Can coincide with Visit 2	1 hour
	*Visit 4	Review pump and CGM data & compliance assessment & Randomisation	After 4 weeks of Visit 3	1-2 hours
Control Intervention (4 months)	*Visit 14	Control therapy initiation at CRC or remotely - Sensor-augmented pump refresher training & competency assessment - HbA1c	After 8 week of end of Visit 13	Up to 6 hours
	*Visit 15	End of first month. Review of home data.	After 4 weeks of Visit 14	<1 hour
	*Visit 16	End of second month; Review of home data. Actiwatch sleep monitor	After 4 weeks of Visit 15	<1 hour
	*Visit 17	End of third month. Review of home data.	After 4 weeks of Visit 16	<1 hour
	*Visit 18	12-lead Holter monitor applied for 5 days.	Within 14 days after Visit 17. Can coincide with Visit 17	<1 hour
	*Visit 19	End of open-loop treatment period (4 months) HbA1c. Revert back to usual pump therapy. Human factor assessment	After 4 weeks of Visit 17	1-2 hours
	-	Washout period	Immediately after Visit 19	4 weeks

CL Intervention (4 months)	*Visit 5	CL initiation at CRC or remotely - CL training & competency assessment - HbA1c	After 4 weeks of end of Visit 19	Up to 6 hours
	* Visit 6	Review use of study devices	After 24-48 hours of Visit 5	<1 hour
	*Visit 7	Review use of study devices	After 1 week of Visit 5	<1 hour
	*Visit 8	Review pump and CGM data	After 1 week of Visit 7	<1 hour
	*Visit 9	End of first month; Review pump and CGM data.	After 4 weeks of Visit 8	<1 hour
	*Visit 10	End of second month; Review pump and CGM data. Actiwatch sleep monitor	After 4 weeks of Visit 9	<1 hour
	*Visit 11	End of third month; Review pump and CGM data.	After 4 weeks of Visit 10	<1 hour
	*Visit 12	12-lead Holter monitor applied for 5 days.	Within 14 days after Visit 11. Can coincide with Visit 11	<1 hour
	*Visit 13	End of closed-loop treatment period (4 months). HbA1c. Collect algorithm device. Revert back to usual pump therapy. Human factor assessment.	After 4 weeks of Visit 11	1-2 hours

\*Could be done via phone / e-mail in UK.

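### Protocol Table 2 (control-first sequence) adds up to an 18-week closed-loop period against the stated 16 weeks, and times its first treatment visit from its last

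*Protocol*

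**What the plan says.** **Period length.** Protocol 9.1 states: "Two 16-week study periods will be performed within four weeks of each other". The synopsis gives 16 weeks of closed-loop without tying it to either treatment order. SAP section 1 describes two 16-week periods.

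**Table 1 (closed-loop first).** Visit 9 is "After 4 weeks of Visit 5", and Visits 10, 11 and 13 follow at four-week steps.

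**Table 2 (control first).** Visits 7 and 8 are one and two weeks after Visit 5. Visit 9 is "After 4 weeks of Visit 8", and Visits 10, 11 and 13 again follow at four-week steps. The Visit 9 row is labelled "End of first month; Review pump and CGM data" and the Visit 13 row "End of closed-loop treatment period (4 months). HbA1c. Collect algorithm device. Revert back to usual pump therapy".

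**Section 9.11** places Visits 9, 10 and 11 at weeks 4, 8 and 12 counted from Visit 5.

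**Start of the first period.** Table 2 times Visit 14, the first visit after randomisation in that sequence, as "After 8 week of end of Visit 13". For the other sequence, Table 1 times Visit 5 as "Can be combined with Visit 4, or within 2 week of Visit 4". Section 7.2, without regard to sequence, says: "Randomisation will take place within 1 week before the start of first home study phase".

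**The concern.** Table 2 is the operating schedule for one of the two randomised sequences, and its timing column is what a site would use to book visits. If that column is followed, closed-loop runs longer than control, and longer than closed-loop in the other sequence.

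- **HbA1c.** The 16-week HbA1c is a key secondary endpoint in the fixed-sequence testing list. It would be taken at about week 18 in one treatment-by-sequence cell. SAP 7.3 accepts samples within 14 days of the end of treatment visit, so its window moves with the visit and the late sample passes unnoticed.
- **Other assessments.** The Actiwatch (Visit 10), the Holter (Visit 12) and the Visit 13 surveys would each move two weeks later in that cell.
- **Safety.** SAP 8.3 counts events from the initiation visit to the end of treatment visit. Its comparison of binary outcomes and its per-subject event counts have no stated adjustment for exposure.

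Separately, the Visit 14 cell cannot be followed at all, because it depends on a visit that happens later.

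**Working it through.** **1. Reproduce the stated 16 weeks.** Weeks are counted from the start of each treatment.

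| Cell | Visits and weeks | End |
|---|---|---|
| Table 1, closed-loop | V9 = 0+4 = 4; V10 = 8; V11 = 12; V13 = 16 | day 112 |
| Table 1, control | V15 = 4; V16 = 8; V17 = 12; V19 = 16 | day 112 |
| Table 2, control | V15 = 4; V16 = 8; V17 = 12; V19 = 16 | day 112 |
| Table 2, closed-loop | V7 = 1; V8 = 2; V9 = 2+4 = 6; V10 = 10; V11 = 14; V13 = 18 | day 126 |

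Three cells reproduce the stated length and one does not. The excess is 126 − 112 = 14 days, and 126/112 = 1.125, so 12.5% longer. The discrepancy comes from a single anchor: counting Visit 9 in Table 2 from Visit 5, as Table 1 and section 9.11 do, gives weeks 4, 8, 12 and 16.

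**2. Visit 14 in Table 2.** In that sequence Visit 13 comes 16 (control) + 4 (washout) + 18 (closed-loop) = 38 weeks after Visit 14, or 36 weeks with a 16-week closed-loop period. Visit 14 therefore cannot follow Visit 13. The 8 weeks would not fit the other sequence either, where Table 1 has 4 weeks between these visits.

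**3. Upper bound on the effect.** Assumptions: 36 randomised, an equal split (18 per sequence, from the 1:1 ratio in SAP section 1), and every control-first participant following the literal timing.

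- **Exposure.** Closed-loop: 18×16 + 18×18 = 612 person-weeks. Control: 36×16 = 576. Ratio 612/576 = 1.0625.
- **HbA1c window (SAP 7.3).** 126 ± 14 gives days 112–140 in the one cell; 112 ± 14 gives days 98–126 in the other three.
- **Actiwatch.** Week 10 instead of week 8.
- **Holter application (0–14 days after the preceding visit in both tables).** Days 98–112 instead of days 84–98.
- **Any-event safety outcome, no true treatment effect.** With a constant rate r per year, P(at least one event) = 1 − exp(−r × days/365.25).
  - r = 1 (the severe hypoglycaemia rate for the average patient in Protocol section 4): 112 days gives 0.264 and 126 days gives 0.292. The closed-loop mean over sequences is 0.278, so the difference from control is 0.0138, and 0.0138 × 36 = 0.50 subject.
  - r = 0.1 (assumed, to show the range): 0.0302 and 0.0339, mean 0.0321, difference 0.0019, × 36 = 0.07 subject.

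The lower bound on every item is zero, reached if sites work from the row labels or the other sections.

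**4. What is not affected.** SAP 4.1 stops CGM data at 112 days after initiation or at the end of treatment visit, whichever is earlier, so the primary and other CGM endpoints cover at most 16 weeks in every cell. Severe hypoglycaemia and DKA incidence rates use person-years.

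**The case against.** The strongest reply is that this is a slip which the rest of the protocol corrects. Most of that stands. The synopsis gives 16 weeks for closed-loop in either order, section 9.11 counts from the start of closed-loop, and the affected rows carry labels that fit 16 weeks. Table 2 cannot be followed literally throughout anyway, so sites must consult other text.

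Four stronger readings are tempting, and the documents do not support them:

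- **Nothing corrects Table 2 for the control-first sequence.** A reader might infer this because section 9.6 introduces what follows as the closed-loop-first situation. But it speaks only of the next section, and section 9.11 uses an anchor that works in either order. Even if the limit were read more widely, the synopsis and section 9.1 would still give 16 weeks.
- **The control-first start is undefined.** Section 7.2 gives an interval for either sequence, and section 9.15 describes Visit 14 as similar to Visit 5. The difference between 1 week in section 7.2 and up to 2 weeks in Table 1 is real but is not a defect of Table 2.
- **The Holter would miss its specified month.** Application on days 98–112 still starts within the fourth month (days 84–112), although a recording begun late could run past day 112.
- **The safety bias is material.** The rate of one event per year describes the average patient, whereas this trial excludes people with more than one severe episode in six months. The comparison is also run only if enough events occur.

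The HbA1c excess is no larger than the plan's own 14-day tolerance. What remains is that the tolerance is centred on the visit, so it cannot detect a systematic shift in one cell.

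**Conclusion.** Table 2 is wrong as written in two places. Its closed-loop visits add to 18 weeks against the stated 16, and its Visit 14 timing is impossible. Both follow from adding up the table and need no assumption.

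The consequence is minor and conditional. It is probably a drafting error with no effect in practice. If it is followed by all control-first participants, closed-loop is 14 days longer in one sequence only, and the key secondary HbA1c is taken at about week 18 in that cell. The documents give no time course for HbA1c, so that shift cannot be sized. The any-event safety comparison would move by at most about 0.5 subject of 36 at one event per year. A reader might infer that the primary result is at risk; the 112-day cap rules that out for the period-length error.

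**What to change.** Reconcile the Table 2 timings for Visit 9 (and through it Visits 10 to 13) and for Visit 14 with sections 7.2, 9.1 and 9.11, the synopsis and Table 1, so that the schedule and the stated period length agree in both sequences. The sponsor should settle the interval from randomisation to the first period in the same edit, since section 7.2 and Table 1 differ.

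The cost is a correction to one schedule table and its cross-references. It needs no new visits, samples or analyses.
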